6.4.2.4 Cycle 1 Day 35 (\pm 7 days) (BM recovery)

- Physical examination and vital signs
- ECOG performance status
- AE monitoring
- Concomitant medication review
- CBC and clinical chemistry panel
- BM biopsy and aspirate for MRD assessment via next-generation sequencing (NGS) and FLT3 mutation testing via PCR

CONFIDENTIAL

6.4.2.5 **Cycle 2, Days 1 and 3 (if applicable)**

- Physical examination and vital signs
- ECOG performance status
- AE monitoring
- Concomitant medication review
- CBC and clinical chemistry panel
- CPX-351 (Days 1 and 3)
- ECG (Day 3)

6.4.2.6 **Cycle 2, Day 6**

- Physical examination and vital signs
- ECOG performance status
- AE monitoring
- Concomitant medication review
- CBC and clinical chemistry panel
- ECG and QTcF assessment (if QTc \leq 470 msec, resume quizartinib)
- Quizartinib (begin daily until Day 21)

6.4.2.7 **Cycle 2 Days 14 and 21**

- ECG

6.4.2.8 **Cycle 2, Day 35 (\pm 7 days)**

- Physical examination and vital signs
- ECOG performance status
- AE monitoring
- Concomitant medication review
- CBC and clinical chemistry panel
- BM biopsy and aspirate with FLT3 mutation testing via PCR
- MRD assessment with BM biopsy and aspirate via NGS

6.4.3 **alloHCT or other CT intervention (within the 30-60 day time period between consolidation and maintenance treatment)**

- Physical examination and vital signs

CONFIDENTIAL

- ECOG performance status
- AE monitoring
- Concomitant medication review
- CBC and clinical chemistry panel
- BM biopsy and aspirate with FLT3 mutation testing via PCR (~ Day 30)
- MRD assessment with BM biopsy and aspirate via NGS

6.4.4 Maintenance Phase

The maintenance phase consists of quizartinib monotherapy once daily in 28-day cycles for a total of 24 cycles or until disease relapse. Maintenance dosing of quizartinib PO will begin at 30 mg/day on Days 1-14, and if there are no toxicities and QTcF is maintained ≤ 450 msec, the dose will increase to 60 mg/day on Day 15. The following procedures and tests will be performed at these visits:

- Serum pregnancy test once every 3 cycles during the maintenance phase

6.4.4.1 Cycles 1-24, Days 1 and 15

- Physical examination and vital signs
- ECOG performance status
- AE monitoring
- Concomitant medication review
- CBC and clinical chemistry panel
- BM biopsy and aspirate with FLT3 MRD NGS mutation testing (Day 24 ± 3 days) at Cycle 3, 6, 12 and 24
- ECG and QTcF assessment (if QTcF ≤ 470 msec, continue quizartinib; if QTcF > 470 msec, see Appendix F)

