Study Drug, Dose, and Mode of Administration:	
Induction phase: CPX-351 (daunorubicin 44 mg/m² IV and cytarabine 100 mg/m² IV) will be given on Days 1, 3, and 5 followed by 30 mg quizartinib by mouth (PO) once daily on Days 8-21. Patients with an incomplete response, but a >50% reduction in the blast count/cellularity ratio compared to the most recent bone marrow (BM) biopsy prior to treatment, should receive one additional cycle of induction therapy (re-induction) with CPX-351 (daunorubicin 44 mg/m² IV and cytarabine 100 mg/m² IV) on Days 1 and 3 only. Re-induction will begin after a 72-hour washout period from the last dose of quizartinib. During re-induction, treatment with quizartinib will resume on Day 6 and continue through Day 21. Any patient with neutropenia or thrombocytopenia lasting ≥ 56 days from the initiation of CPX-351 will not receive consolidation and will instead proceed to the maintenance phase.
 
Consolidation phase: At the Investigator's discretion, patients who achieve CR and do not proceed to an alloHCT or other CT intervention will proceed to the consolidation phase beginning 7 days (± 7) after neutrophil recovery (ANC >1000/μL). Administer up to 2 consolidation cycles of CPX-351 (daunorubicin 29 mg/m² IV and cytarabine 65 mg/m² IV) on Days 1 and 3. Begin quizartinib 30 mg PO once daily on Days 6-21.
 
Maintenance phase: Maintenance dosing of quizartinib will begin at 30 mg/day on Days 1-14, and if there are no non-hematologic Grade ≥ 3 toxicities, the quizartinib dose will increase to 60 mg/day on Day 15. The maintenance phase is a 28-day cycle beginning 7 days (± 7) after neutrophil recovery (ANC >1000/μL) from the consolidation phase or induction phase. Patients will receive quizartinib once daily for a total of 24 cycles or until disease relapse

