5. STUDY DESIGN

This is a multi-center, non-randomized, open-label, two-part prospective Phase II clinical trial in patients with relapsed or refractory FLT3-ITD mutation-positive AML. The study is designed to assess the safety and tolerability as well as the efficacy of administering CPX-351 (cytarabine:daunorubicin liposome complex) with quizartinib, a second-generation FLT3 inhibitor. The plan for administration is divided into three phases: induction, consolidation, and maintenance. Approximately 34 patients are planned to be screened and enrolled. Patient participation is expected to be 4 years.

A total of 10 patients will be enrolled in the safety lead-in. The safety lead-in portion of the study is designated as Part 1. If >3 patients experience delayed neutrophil count recovery >56 days from the first day on the study regimen, or delayed thrombocytopenia recovery >56 days from the first day on the study regimen, or if >3 patients develop a non-hematologic toxicity, defined as a Grade 4 non-hematologic adverse event determined to be probably related to the combined treatment, or a Grade 4 neutropenia, then the study will be terminated.

Assuming safety parameters are met, the first 10 patients will be followed for response in the Part 2 of the study. An additional 24 patients will be enrolled in Part 2 of the study (induction, consolidation and maintenance). All patients will be assessed for response.

Patients who fail to respond to therapy will be followed until a new therapy is instituted. . Patients who experience an AE that results in the discontinuation of study treatment will be

[figure not shown]
CONFIDENTIAL

STUDY DRUG: QUIZARTINIB
PROTOCOL DATE: 10 AUGUST 2020

DEVELOPMENT INNOVATIONS STUDY NUMBER: AML 48
VERSION 4.0

followed until resolution/stabilization for AEs attributed to the medication. Outcomes for all patients will be assessed for 24 months from the date of last treatment.

Figure 1 Study Schema

*All treatment phases follow a 28-day cycle. Induction and re-induction consist of: CPX-351 (liposomal daunorubicin 44 mg/m² IV and cytarabine 100 mg/m² IV) + quizartinib 30 mg PO QD. The maintenance phase: begin quizartinib 30 mg PO QD on Days 1-14. If there are no toxicities and QTcF is maintained ≤ 450 msec, increase dose to 60 mg QD on Day 15.

[†]For one cycle

[‡]For up to two cycles

CONFIDENTIAL

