5.2.4 Maintenance Phase

The maintenance phase consists of 28-day cycles. Patients will receive quizartinib once daily for a total of 24 cycles or until disease relapse. Maintenance dosing of quizartinib will begin at 30 mg PO once daily on Days 1-14, and if there are no non-hematologic Grade ≥ 3 toxicities and QTcF is maintained ≤ 450 msec, the quizartinib dose will increase to 60 mg/day on Day 15. If consolidation therapy is not advised at all or if only 1 cycle of consolidation is advised based on prolonged toxicities, maintenance therapy will begin 7 days (± 7) after neutrophil recovery (ANC $> 1000/\mu\text{L}$) from the consolidation phase or induction phase.

Patients who proceed to alloHCT or other CT intervention after consolidation will resume quizartinib maintenance no earlier than Day 30 from the intervention or transplant. If ≥ 2 CT interventions (e.g., repeat DLI) are planned after maintenance, a 28-day hold is acceptable, with resumption of quizartinib with the next cycle. If the patient is on quizartinib prior to HCT or CT intervention, quizartinib should be discontinued 7 days prior if a conditioning therapy is utilized. If proceeding to a CT intervention without conditioning therapy (e.g., DLI), quizartinib should be discontinued one day prior to CT intervention.

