- d **Maintenance:** Maintenance dosing of quizartinib will begin at 30 mg/day on Days 1-14, and if there are no toxicities and QTcF is maintained ≤450 msec, will increase to 60 mg/day on Day 15. The maintenance phase is a 28-day cycle beginning 7 days (± 7 days) after neutrophil recovery from the consolidation phase or induction phase. Patients will receive quizartinib once daily for a total of 24 cycles or until disease relapse. Patients who proceed to alloHCT or other CT intervention **after** consolidation will resume quizartinib maintenance 30-60 days from the intervention for a total of 24 cycles or until disease relapse. If the patient is on quizartinib prior to HCT or CT intervention, quizartinib should be discontinued 7 days prior if a conditioning therapy is utilized. If ≥2 CT interventions (e.g., repeat DLI) are planned after maintenance, a 28-day hold is acceptable, with resumption of quizartinib with the next cycle (see Section 5.2.4).
- e Informed consent must be obtained prior to the initiation of any screening test or procedure.

CONFIDENTIAL

STUDY DRUG: QUIZARTINIB
 PROTOCOL DATE: 10 AUGUST 2020

DEVELOPMENT INNOVATIONS STUDY NUMBER: AML 48
 VERSION 4.0

- f The screening medical history, physical examination, vital signs, ECOG performance status, and triplicate ECGs, TTE/MUGA, baseline signs and symptoms and safety laboratory tests (including pregnancy and virus testing [hepatitis serology (Hepatitis B surface antigen and antibody and Hepatitis C antibody), HIV-1, 2]) should be done following written consent and prior to initiation of therapy.
- g Physical examination will include measurements of height (screening only) and weight.
- h Vital signs will include resting heart rate, blood pressure, respiratory rate, and temperature.
- i Patients will receive a lumbar puncture during pre-transplant workup, per institutional practices and following site-specific standard operating procedures within the first 2 weeks on study treatment. No further intrathecal (IT) chemotherapy is required in this study if there is no evidence of disease. In patients who have CNS disease involvement, IT chemotherapy should continue every 4 days (± 1 day) until disease clearance, followed by every 7 days (± 2 days) for 2 additional administrations. Thereafter, administer IT chemotherapy every 28 days (± 7 days) for at least 12 cycles (see Section 6.3).

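### The condition for raising quizartinib from 30 to 60 mg/day on Day 15 of maintenance is stated three different ways in the current protocol

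*Combined protocol and SAP*

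**What the plan says.** All five statements agree on the dose steps: 30 mg/day on Days 1 to 14 of maintenance, then 60 mg/day from Day 15. They differ on who qualifies.

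- **Synopsis (study drug, dose and mode of administration):** "if there are no non-hematologic Grade ≥ 3 toxicities, the quizartinib dose will increase to 60 mg/day on Day 15". No QTcF limit is given.
- **Section 5.2.4:** "if there are no non-hematologic Grade ≥ 3 toxicities and QTcF is maintained ≤ 450 msec".
- **Section 6.4.4:** "if there are no toxicities and QTcF is maintained ≤ 450 msec, the dose will increase to 60 mg/day on Day 15". The operative words, "if there are no toxicities and QTcF is maintained", name no grade or type of toxicity.
- **Figure 1 note (Section 5):** "If there are no toxicities and QTcF is maintained ≤ 450 msec, increase dose to 60 mg QD on Day 15".
- **Appendix D, footnote d:** "if there are no toxicities and QTcF is maintained ≤450 msec, will increase to 60 mg/day on Day 15". This footnote refers the reader to Section 5.2.4, whose toxicity condition is different.

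Section 5.1 says that patients are treated under the plan in Section 5.2. No section states which wording takes precedence if two of them disagree. All five statements are in the current text of Version 4.0, so this is not a difference between the amendment summary and the text in force.

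**The concern.** A site must decide at Day 15 whether a patient moves to 60 mg/day, and two body sections of the same protocol give different tests. A decision that complies with one section can be a deviation under another.

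The dose matters for the trial's own aims. Safety and tolerability is a primary objective (Section 2.1), and tolerability of quizartinib after alloHCT or DLI is a secondary one (Section 2.2). Section 1.5 describes QT prolongation with quizartinib as dose dependent. Section 7.5.1 reports Grade 2 or higher QTcF prolongation in 11% of patients at 30 mg and 17% at 60 mg in a randomized Phase II monotherapy study. About 5 sites are planned, and maintenance can run for 24 cycles. If sites follow different sections, the pooled maintenance safety data will mix escalation rules, and so will the exposure behind DOR, EFS and OS.

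**Working it through.** No sample size, power or event count is involved, so the check is a comparison of texts.

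**Step 1: split each rule into its parts.**

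| Place | Toxicity that blocks the increase | QTcF limit |
|---|---|---|
| Synopsis | Non-hematologic, Grade ≥3 | None stated |
| Section 5.2.4 | Non-hematologic, Grade ≥3 | ≤450 msec |
| Section 6.4.4 | Any, no grade or type given | ≤450 msec |
| Figure 1 note | Any, no grade or type given | ≤450 msec |
| Appendix D, footnote d | Any, no grade or type given | ≤450 msec |

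The QTcF limit is present in four places and absent in one. The toxicity condition is worded one way in two places and another way in three. That gives three distinct rules.

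**Step 2: apply each rule, read literally, to simple patient profiles.**

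| Profile at Day 15 | Synopsis | 5.2.4 | 6.4.4, Figure 1, Appendix D |
|---|---|---|---|
| No toxicity, QTcF ≤450 | Increase | Increase | Increase |
| Grade 1–2 non-hematologic only, QTcF ≤450 | Increase | Increase | No increase |
| Hematologic only, QTcF ≤450 | Increase | Increase | No increase |
| No other toxicity, QTcF 451–480 | Increase | No increase | No increase |
| Non-hematologic Grade ≥3 | No increase | No increase | No increase |

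Three of the five profiles are classified differently, and every pair of rules disagrees on at least one profile.

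**Step 3: does the synopsis toxicity condition already cover QTcF?** Section 8.1 treats QTcF prolongation as one of the non-hematologic toxicities. The synopsis condition could therefore block the increase for QTcF, but only from Grade 3, which Appendix F places above 500 msec. Values above 450 and up to 500 msec remain outside it. In the upper part of that band, above 480 msec, Appendix F separately calls for a dose reduction, so the clearest gap is 451 to 480 msec.

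**Step 4: do neighbouring rules settle it?** Section 6.4.4.1 uses 470 msec, but for continuing quizartinib, not for increasing it. Section 5.3.2 has a Day 15 step for patients who were on a strong CYP3A4 inhibitor at enrollment. It goes from 20 to 30 mg/day and concerns another group, so it is not a fourth version of this rule.

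**Step 5: is the primary efficacy test affected?** Section 10.4.2 reads response at the recovery assessment, before maintenance begins. The ORR test does not depend on the Day 15 decision.

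**The case against.** The best defence is that the protocol does point to a governing text. Section 5.1 sends treatment to Section 5.2, footnote d cites Section 5.2.4, and the other statements are a synopsis, a figure note, a schedule footnote and the lead-in to a list of visit procedures. On that view Section 5.2.4 holds the full rule and the rest are loose paraphrases. This carries some weight as a guide to intent. It sets no precedence, however, and Section 6.4.4 is a body section that site staff will use at the visit itself.

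A second defence concerns consequences, and much of it stands.

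- A reader might infer that almost nobody would reach 60 mg under the any-toxicity wording and most patients would under the other. The documents give no figure for either. The wording may also mean toxicity arising during the 14 days at 30 mg, which excludes residual effects of chemotherapy. Maintenance outside the transplant route generally starts after ANC exceeds 1000/μL, which removes some neutropenia, although it says nothing about platelets. The rates in Section 7.5.2 for prolonged thrombocytopenia (28%) and neutropenia (17%) after CPX-351 induction refer to counts beyond Day 42 of induction, not to Day 15 of maintenance, and cannot be used as the affected share.
- A reader might infer that the synopsis instructs sites to escalate despite a QTcF above 450 msec. An omission from a summary is not a contrary instruction. Four other statements carry the limit, ECGs are scheduled on Days 1 and 15 of maintenance cycles, and Appendix F actions apply. For Grade 1, Appendix F keeps the dose the same, but it gives no msec range for that grade and does not mention the Day 15 step. None of this supplies the 450 msec limit, so the omission still needs correcting.
- A reader might infer that dosing will differ between sites. The documents show only that it could.

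**Conclusion.** The contradiction is real: five statements, three rules, and no order of precedence. It is an internal inconsistency, not a debatable design choice. It changes the classification of patients with only Grade 1–2 non-hematologic toxicity, only hematologic toxicity, or QTcF above 450 msec but not Grade 3.

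The number of patients affected cannot be derived from the documents. It could be many if the any-toxicity wording is applied literally and residual or low-grade effects count; that is an assumption. What could be affected is maintenance exposure, QT safety, the primary safety and tolerability objective, and the interpretation of DOR, EFS and OS. The documents do not support extending the point to the primary response-rate test.

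**What to change.** Bring the synopsis, the Figure 1 note, Section 5.2.4, Section 6.4.4 and Appendix D footnote d to one escalation condition. The agreed text should state:

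- which grade and type of toxicity counts;
- over what period it is counted;
- whether QTcF is part of the condition and, if so, the limit.

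The sponsor's clinical team must choose the condition; this review takes no position on which wording is right. Once one statement is settled, the other four can repeat it word for word or simply refer to it. The cost is protocol amendment wording, with no change to sample size or to the response-rate test.

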6.4.5 End of Treatment/Early Termination Visit

Patients will complete the study at the time of PD, if they withdraw consent, if they withdraw due to an AE, or at the time the study is terminated. If either study treatment or patients are discontinued, the reason will be recorded in the eCRF and source document. Patients who are removed from treatment for reasons other than death or disease progression (PD) are considered to be patients who have terminated early. Reasons for discontinuation include one of the following: AEs, protocol violation, patient withdraws consent, patient is lost to follow-up, administrative reasons (including study closure), death, or other. Patients who complete or discontinue from the study should have the following study completion/early withdrawal evaluations performed as soon as possible after the day of study completion/early withdrawal.

- Physical examination and vital signs

CONFIDENTIAL

STUDY DRUG: QUIZARTINIB
 PROTOCOL DATE: 10 AUGUST 2020

DEVELOPMENT INNOVATIONS STUDY NUMBER: AML 48
 VERSION 4.0

- ECOG performance status
- AE monitoring
- Concomitant medication review
- CBC and clinical chemistry panels
- BM biopsy and aspirate with FLT3 mutation testing, if applicable
- ECG and QTcF assessment, if applicable

Patients prematurely discontinuing from the study must be followed for AE and concomitant medication use for 30 days following the last administration of study drugs or until resolution/stabilization of an ongoing AE attributed to the medication.

Patients who discontinue from the study may be treated with other therapies at the discretion of the Investigator.

6.4.6 Long-Term Follow-up

A formal end-of-study visit will be performed every 6 months for 2 years post-study treatment. The following procedures and tests will be done:

- Disease response assessment per CIBMTR classification (Appendix E)
- Survival status

6.5 Study Assessments

6.5.1 Medical History and Demographics

A complete medical history will be taken. Information to be documented includes demographics, prior medical illnesses and conditions, prior surgical procedures, date and stage of original diagnosis and details of prior chemotherapy/radiotherapy administered and other treatments for cancer (including type of drugs, dosages, schedule or administration, response and response duration).

6.5.2 Physical Examinations (Including Performance Scale and Vital Signs)

A complete physical examination will be done at baseline, at each visit, at the end-of-treatment visit, and long-term follow-up visit as well as at the discretion of the Investigator. Examinations will include documentation of height (at screening only), weight, vital signs, and ECOG performance status (Appendix A). Any abnormal or clinically significant findings from the physical examination must be recorded on the appropriate eCRF page.

6.5.3 12-Lead Electrocardiogram

Triplicate ECGs recording will be performed according to Appendix D and at the discretion of the Investigator. Each will be performed with the patient in a supine position having rested in this position for at least 5 minutes before the reading. If QTcF prolongation develops from the time of initial screening to the day of quizartinib administration (i.e. Day +8 of induction), concomitant medications, and electrolytes should be assessed for a reversible cause. ECGs may

CONFIDENTIAL

STUDY DRUG: QUIZARTINIB
 PROTOCOL DATE: 10 AUGUST 2020

DEVELOPMENT INNOVATIONS STUDY NUMBER: AML 48
 VERSION 4.0

be repeated daily for up to 3 days from the original start date to assess for correction and to meet the eligibility criteria to administer quizartinib (see Section 3.2).

6.5.4 **Cardiac Echocardiogram**

A TTE or MUGA will be obtained upon enrollment, prior to initiation of treatment, and within 1 week prior to consolidation treatment (Day 1).

6.5.5 **Pregnancy Testing**

In women of child-bearing potential, a serum beta human chorionic gonadotropin pregnancy test must be done 72 hours prior to the start of treatment. Serum Pregnancy tests are also required prior to the start of each cycle during the induction and consolidation phases, during maintenance phase a serum pregnancy test will be obtained once every 3 cycles.

6.5.6 **Laboratory Assessments**

Laboratory samples (CBC, clinical chemistry, urinalysis, and virology) are to be collected as outlined in Appendix D. Laboratory results will be graded using NCI CTCAE Version 5.0.

6.5.7 **FLT3 Mutation PCR Testing**

The presence of the FLT3-ITD mutation will be detected using PCR from bone marrow aspiration samples collected with all planned BM samples. Next-generation sequencing of MRD by FLT3-ITD mutational analysis will be performed with all planned BM biopsies, excluding screening and the Day +21 induction response assessment. The presence of FLT3-ITD for inclusion is defined as positive if the PCR assay detects tandem duplication at 3% or higher.

6.5.8 **Response and Activity Assessments**

See Section 6.5.11 and Section 9.

6.5.9 **Adverse Event Assessments**

Information regarding the occurrence of AEs, including infections, will be collected from the time the patient signs the ICF throughout their participation in the study, including a period of 30 days after the last dose of study drug. Adverse event severity will be determined using the CTCAE Version 5.0 grading scale. See Section 11 for more details.

6.5.10 **Prior and Concomitant Medications**

All concomitant medications are to be collected and recorded from the time the patient signs the ICF and throughout the patient's participation in the study.

6.5.11 **Bone Marrow Aspirates and Biopsies**

Response assessment by BM biopsies and aspirates will be collected at Day 21 (± 2 days) of induction (and re-induction therapy, if applicable), as well as at the time of count recovery after CPX-351 + quizartinib, defined as obtaining a BM biopsy within 4 days of having an ANC $>500\mu\text{L}$ for ≥ 24 hours (at Day 35 [± 7 days] during induction and consolidation therapy). Bone marrow biopsies and aspirates will also be collected after Cycles 3, 6, 12, and 24 in the maintenance phase. Thereafter, assessment of disease status will be at the discretion of the primary treating hematologist/oncologist.

CONFIDENTIAL

All biopsies will include monitoring for FLT3 mutation by PCR. Additional studies, including fluorescence in situ hybridization (FISH), cytogenetics, and/or molecular analyses, should be obtained based upon known mutations at the discretion of the physician.

